Procedure Title: TREAT GRX Study Protocol

Doc Number: 104-09062

Revision: A

Page: 6 of 34

# TREAT GRX STUDY SUMMARY

TITLE	An Evaluation of Performance of the CorPath ® GRX System in Robotic-PCI during Acute STEMI
SHORT TITLE	TREAT GRX Study
DEVICE	
 
CorPath® GRX System:
 
Bedside Unit consists of the Extended Reach Arm, Robotic Drive, and single-use Cassette.
 
Interventional cockpit
 
Control console
 

REGULATORY STATUS	The CorPath GRX System was granted 510(k) clearance (K160121) on October 27, 2016.
INDICATION FOR USE	The CorPath GRX System is intended for use in the remote delivery and manipulation of guidewires and rapid exchange catheters, and remote manipulation of guide catheters during percutaneous coronary and vascular procedures.
STUDY OBJECTIVE	This study will evaluate the performance of the CorPath GRX System in Robotic Primary PCI (RPPCI) in the treatment of STEMI.
STUDY DESIGN	This is a prospective, post-market, single-arm, multi-center, observational study to evaluate the performance of the CorPath GRX System during robotic-PCI for acute ST elevation myocardial infarction (STEMI).
PRINCIPAL INVESTIGATOR	[name], DO, MA, FACC, FSCAI Interventional Director, Short Term Mechanical Circulatory Support Program WellStar Health System [name] USA
SAMPLE SIZE	Up to 100 subjects shall be enrolled in the study.
INVESTIGATIONAL SITES	A maximum of five (5) sites may participate.

Procedure Title: TREAT GRX Study	
Protocol	
Dec Number: 101 09062	

Doc Number: 104-09062

Revision: A

Page: 7 of 34

EVALUATION PERIOD	Estimated date of first patient enrolled: August 2020 Anticipated enrollment period: 12 months Estimated date of last patient enrolled: August 2021
STUDY DURATION/ FOLLOW-UP PERIOD	All subjects will be followed post-CorPath GRX PCI procedure through 72-hours post-procedure or hospital discharge, whichever occurs first.
SUBJECT POPULATION	Subjects with a clinical indication of STEMI.
INCLUSION CRITERIA	Candidates will be included in the study only if all the following conditions are met:
	
 
Age ≥18 and ≤ 80 years
 
Patients with STEMI<12 h of symptom onset
 
Patient deemed appropriate for robotic-assisted PCI
 
The subject has been informed of the nature of the study, agrees to its provisions, and has provided written consent
 

EXCLUSION CRITERIA	Candidates will be excluded from the study if any of the following conditions are present:
	
 
Cardiogenic shock
 
Cardiac arrest
 
Need for manual or mechanical thrombectomy
 
Failure/inability/unwillingness to provide informed consent
 
The Investigator determines that the subject or the coronary anatomy is not suitable for robotic-assisted primary PCI treatment
 

PRIMARY ENDPOINT	Time from Catheterization Lab Arrival to Device Activation (CLADA) by CorPath GRX System.

#### Procedure Title: TREAT GRX Study Protocol Doc Number: 104-09062

**Revision:** A

Page: 8 of 34

#### SECONDARY ENDPOINTS

# Freedom from MACE events

Completion of the STEMI procedure without in-hospital major adverse cardiovascular event MACE). MACE is defined as cardiac death, clinically driven target vessel revascularization (TVR) by repeat PCI, surgical bypass for any segment of the target vessel or stent thrombosis.

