## **Technical success**

Completion of the PCI procedure entirely robotically or with partial manual assistance.

Procedure Title: TREAT GRX Study Protocol

Doc Number: 104-09062

**Revision:** A

Page: 9 of 34

be

	Serious adverse events All Serious Adverse Events (SAEs) from the start of the CorPath GRX procedure until the end of the study will be summarized.
STUDY SPONSOR	Corindus, Inc. [name] USA
MANUFACTURER	Corindus, Inc. [name] USA
DATA COORDINATING CENTER	MedNet Solutions, Inc. [name]
MONITORING SERVICE	Corindus, Inc. [name] USA
STATISTICAL ANALYSIS SERVICES	TBD

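### MACE is defined over the whole hospital stay, but required follow-up ends at 72 hours or discharge, so late in-hospital events fall inside the endpoint and outside observation

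*Protocol*

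**What the plan says.** In the Protocol's Secondary Endpoints, under Freedom from MACE events, the endpoint is "Completion of the STEMI procedure without in-hospital major adverse cardiovascular event MACE". The components follow: "MACE is defined as cardiac death, clinically driven target vessel revascularization (TVR) by repeat PCI", then surgical bypass of the target vessel and stent thrombosis. No component carries a time limit, so the only window is the hospital stay.

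The Study Summary, in the row on study duration and follow-up, says: "All subjects will be followed post-CorPath GRX PCI procedure through 72-hours post-procedure or hospital discharge, whichever occurs first".

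The last secondary endpoint covers serious adverse events: "All Serious Adverse Events (SAEs) from the start of the CorPath GRX procedure until the end of the study will be summarized".

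On size, the Study Summary says "Up to 100 subjects shall be enrolled in the study". The design is single-arm, with at most five sites. The primary endpoint is "Time from Catheterization Lab Arrival to Device Activation (CLADA) by CorPath GRX System".

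**The concern.** The endpoint runs to discharge, whereas follow-up can stop before discharge. The two windows agree for a short stay and disagree for a long one. The 72-hour clause has an effect only for subjects still in hospital at that time, so the protocol itself foresees the group in which its two statements conflict.

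Three things are at stake:

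- **Bias.** If a subject still admitted at 72 hours is counted as event-free, a missed event moves the MACE-free rate in one direction only, upward.
- **Uneven ascertainment.** One site may record an event on day 4 while another closes the case at 72 hours. Both could claim to follow the protocol.
- **Comparability.** A single-arm study has no concurrent control cut off at the same time. A rate labelled in-hospital but truncated at 72 hours is not like-for-like with one collected to discharge.

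This cannot be left to the SAP. An SAP can decide how to classify subjects still admitted at 72 hours, but it cannot supply events that nobody was asked to collect.

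**Working it through.** The protocol pages available state no figure to reproduce for this endpoint: no MACE rate, performance goal, alpha or power. The check is a comparison of two windows, followed by an illustration of size.

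**Inputs from the Protocol.** Endpoint window: hospital stay, no hour limit (Freedom from MACE events). Follow-up: the earlier of 72 hours and discharge (Study Summary). Sample size: at most 100 (Study Summary).

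**Step 1: the windows.** Let D be the time of discharge in hours after the procedure.

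- Endpoint window: 0 to D.
- Observation window: 0 to min(72, D).
- Unobserved endpoint time: max(0, D − 72).

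Discharge at 48 h leaves 0 h unobserved, discharge at 96 h leaves 96 − 72 = 24 h, and discharge at 120 h leaves 120 − 72 = 48 h.

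**Step 2: does another provision close the gap?** Serious adverse event reporting runs to the end of the study, and the only duration stated is the same follow-up period. It therefore does not extend past 72 hours for any subject. Nothing else in the pages available extends MACE collection to discharge or limits MACE to 72 hours.

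**Step 3: one missed event.** With n = 100, one missed event raises the MACE-free rate by 1/100 = 1.0 percentage point.

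**Step 4: effect on the confidence limit.** The event counts here are assumptions. For x observed events in n = 100, the exact (Clopper-Pearson) 95% lower limit for the MACE-free proportion is the 2.5% quantile of a Beta(100 − x, x + 1) distribution.

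| Events x | MACE-free rate | Exact 95% CI |
|---|---|---|
| 1 | 99% | 94.55% to 99.97% |
| 2 | 98% | 92.96% to 99.76% |
| 3 | 97% | 91.48% to 99.38% |
| 4 | 96% | 90.07% to 98.90% |
| 5 | 95% | 88.72% to 98.36% |

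If one of the true events falls after 72 hours and is missed, the lower limit shifts as follows:

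- 2 true, 1 seen: 94.55 − 92.96 = 1.59 points.
- 3 true, 2 seen: 92.96 − 91.48 = 1.48 points.
- 5 true, 4 seen: 90.07 − 88.72 = 1.35 points.

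**Step 5: how many events might be missed.** Again on assumed values, suppose 10% to 40% of 100 subjects stay beyond 72 hours and 0.5% to 2% of those have a later in-hospital MACE. The expected number missed is then between 100 × 0.10 × 0.005 = 0.05 and 100 × 0.40 × 0.02 = 0.8. This is an expected upward error of 0.05 to 0.8 percentage points in the rate.

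**The case against.** The strongest reply is that the passages can be read together. The follow-up rule applies to all subjects and closes no later than discharge, so every MACE it captures does occur in hospital. A general limit may bound an endpoint without being repeated in its definition. On that reading nothing is missed and the defect is one of wording. This reading is possible, but the label would still be wrong for anyone admitted beyond 72 hours, because the reported rate would not cover their hospital stay.

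Second, only the study summary (pages 6 to 9 of 34) is available, and a fuller definition may appear elsewhere. A site might also record a late event without being asked. Both points stand. The claim is limited to the conflict between the two statements: late events are not required to be observed, which is not proof that none will be.

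Third, these pages do not define the end of the study, so the serious adverse event route is not strictly closed. That is fair, but the row heading treats study duration and follow-up period as one, which favours the reading used here.

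Fourth, the upward bias depends on counting subjects as event-free, and censoring or an explicit 72-hour target would not carry it. This is correct. However, required follow-up ends by 72 hours for every subject, so censoring yields a 72-hour quantity and does not recover the in-hospital one.

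Fifth, the size is assumed. One missed event lies above the expected range of 0.05 to 0.8, and the exclusion of cardiogenic shock and cardiac arrest plausibly makes long stays and late events rarer. This stands, and the illustration shows only what one missed event would do, not how likely it is.

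Finally, this is one of 11 secondary endpoints in an observational study, with no MACE hypothesis or threshold in the pages available. That limits the consequence but does not remove the contradiction.

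**Conclusion.** The concern holds. For subjects admitted beyond 72 hours, the endpoint as worded and the follow-up as worded cannot both be met, and nothing in the available pages reconciles them.

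The practical effect may be small or nil and cannot be derived from the protocol. The figures above rest on 100 subjects, on assumed event counts and on counting subjects still admitted at 72 hours as event-free. The primary endpoint, the time from catheterization laboratory arrival to device activation, is untouched. The point should be corrected, with medium confidence because most of the protocol is not available.

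**What to change.** Make the two statements agree, in one of two ways.

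1. **Keep the in-hospital definition and collect to match it.** For subjects who stay beyond 72 hours, ascertain MACE through discharge by chart review. The cost is a short record check at discharge, with no extra visit, and possibly a slightly lower MACE-free rate.
2. **Keep the 72-hour limit and rename the endpoint.** Define it as MACE up to the earlier of 72 hours after the procedure and discharge, and report how many subjects were still in hospital at 72 hours. The cost is a wording change and one extra count, but the result is less comparable with MACE rates collected to discharge.

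Neither option changes treatment, sample size or the primary analysis.

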## First Medical Contact (FMC) to device activation time

Time at which the patient was first evaluated by Emergency Medical System (EMS) or Emergency Department arrival to device activation.

## Access to device activation

Time from initial sheath insertion to device activation.

## Access to wire time

Defined as time measured from sheath insertion to crossing the lesion with the coronary guidewire.

## **Overall procedure time**

Defined as the time measured from sheath insertion to removal of the last device used to treat the culprit lesion.

## Fluoroscopy time

Total fluoroscopy time (min.) utilized during the procedure as recorded by the Imaging System.

## Patient radiation exposure

DAP (dose-area-product) and AK (air kerma) as recorded during the procedure.

## **Contrast fluid volume**

Total contrast volume (mL/cc) used during the procedure.

## **Conversion to manual (Binary)**

Conversion from robotic technique to manual technique due to inability to successfully wire lesion or deliver first device.

## **Technical success**

Completion of the PCI procedure entirely robotically or with partial manual assistance.

Procedure Title: TREAT GRX Study Protocol

Doc Number: 104-09062

**Revision:** A

Page: 9 of 34

be

	Serious adverse events All Serious Adverse Events (SAEs) from the start of the CorPath GRX procedure until the end of the study will be summarized.
STUDY SPONSOR	Corindus, Inc. [name] USA
MANUFACTURER	Corindus, Inc. [name] USA
DATA COORDINATING CENTER	MedNet Solutions, Inc. [name]
MONITORING SERVICE	Corindus, Inc. [name] USA
STATISTICAL ANALYSIS SERVICES	TBD

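### Can a completed case count both as a conversion to manual and as a technical success, and does that require a change?

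*Protocol*

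**What the plan says.** The Study Summary describes the design in these words: "This is a prospective, post-market, single-arm, multi-center, observational study to evaluate the performance of the CorPath GRX System". The objective reads "This study will evaluate the performance of the CorPath GRX System in Robotic Primary PCI (RPPCI) in the treatment of STEMI". On size, "Up to 100 subjects shall be enrolled in the study", and on sites, "A maximum of five (5) sites may participate". The primary endpoint is "Time from Catheterization Lab Arrival to Device Activation (CLADA) by CorPath GRX System".

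Two of the secondary endpoints matter here:

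- **Technical success:** "Completion of the PCI procedure entirely robotically or with partial manual assistance".
- **Conversion to manual (Binary):** "Conversion from robotic technique to manual technique due to inability to successfully wire lesion or deliver first device".

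The text at hand sets no limit on how much manual help still counts as partial. It does not say whether a converted case can be a technical success, and it attaches no target rate, hypothesis or decision rule to either endpoint. It covers pages 6 to 9 of 34, under a study summary heading. The SAP is not at hand.

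**The concern.** The two definitions work on different axes. Conversion is defined by an event and its cause: the robot could not wire the lesion or deliver the first device. Technical success is defined by outcome: the PCI was finished, with the robot doing all or part of the work. A single case can therefore satisfy both.

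That looks awkward in a study of device performance. If completed conversions count as successes, a failure of the robot at an early step is scored in its favour, and technical success drifts towards a plain PCI completion rate. With up to five sites, one could also fear that some count such cases as successes and others do not, so that the pooled rate has no single meaning.

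**Working it through.** **The definitions applied to the possible cases**

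| Case | Conversion? | Technical success? |
|---|---|---|
| Robotic throughout, completed | No | Yes |
| Wire and first device robotic, a later step by hand, completed | No | Yes, expressly allowed |
| Wire robotic, first device by hand after robotic failure, completed | Yes | Yes if read literally; no if a conversion is taken to be more than assistance |
| Robotic wiring fails, everything afterwards by hand, completed | Yes | Doubtful, since little of the treatment was robotic |
| Robotic wiring fails, wired by hand, robotic work resumes, completed | Yes | As in the third row |
| Not completed | Either | No |

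The overlap is clear for conversion at the first device. At the wire it depends on what happens next.

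**Size of the gap.** The protocol states no rate for either endpoint, so there is no figure to reproduce. Let n be the subjects, S those scored as technical successes, C the conversions, and x the subjects scored as both. Removing conversions from the successes lowers the rate by x/n.

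- Per case: 1/100 = 1.0 percentage point at the stated maximum; 1/50 = 2.0 points if only 50 enrol (assumed).
- Illustration with n = 100, 2 cases not completed, and c completed conversions (the last two assumed):

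| c | Counted as success: (100 − 2)/100 | Not counted: (98 − c)/100 |
|---|---|---|
| 2 | 98% | 96% |
| 5 | 98% | 93% |
| 10 | 98% | 88% |
| 15 | 98% | 83% |

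**What the two reported totals reveal.** Even without a cross-tabulation, x cannot exceed C and cannot be less than S + C − n. Take the row c = 10, with neither uncompleted case converted, so C = 10. Then S + C − n = 98 + 10 − 100 = 8, and x lies between 8 and 10. The rate without conversions therefore lies between 88% and 90%.

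**What subject-level data reveal.** If both endpoints are recorded for each subject, the stricter rate is the number of successes without conversion, (S − x)/n. This does not depend on how converted cases were scored. To test it against mixed scoring, assume five sites of 20 subjects, each with 2 completed conversions, and let k sites exclude conversions from success:

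- S = 98 − 2k, that is 98, 96, 94, 92, 90 or 88 for k = 0 to 5.
- x = 2(5 − k) = 10 − 2k.
- S − x = (98 − 2k) − (10 − 2k) = 88 for every k.

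The pooled headline rate could vary by 10 points in this example, but the count of successes without conversion stays at 88.

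**The case for a change.** The strongest case for a change is that the meaning of success belongs in the protocol. Sites need the rule when they record cases, and two separate rates do not show exactly how many subjects are in both. The gap need not be trivial either. If all 100 PCIs were completed and 10 were conversions (assumed), the exact 95% interval would be 96.4% to 100% on the inclusive reading and 82.4% to 95.1% on the exclusive one. The two intervals do not meet. One sentence would settle the matter.

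Part of this stands. The wording does permit double scoring of a first-device conversion, and the summary does not say which reading is meant.

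The rest does not carry a change:

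- The endpoints ask different questions, and nothing requires them to be mutually exclusive. Counting completed conversions as success would be a legitimate choice, so no error is being corrected.
- The usual sense of the words keeps a conversion apart from assistance, and an analyst following it has a workable rule.
- The separate totals bound the overlap, and a cross-tabulation gives it exactly.
- Nothing in the text says that sites score technical success by their own reading. A single data coordinating center is named, so central derivation fits the text equally well.
- A one-time classification into wholly robotic, assisted, converted and not completed would need a further rule, because a case both converted and not completed fits two of the groups.
- The text at hand is a synopsis, and a fuller definition may stand in the later pages or in the SAP.

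**Conclusion.** No change to the plan is needed. The definitions leave one case type open, chiefly a completed case converted at the first device, at 1.0 percentage point per case when n = 100. The total is unknown because the protocol gives no conversion rate; the 2 to 15 point gaps above are arithmetic on assumed counts, and with no completed conversions the gap is zero.

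The consequence is contained. Technical success is a descriptive secondary endpoint in a single-arm study, with no target attached in the text at hand. Conversion is visible beside it, and the stricter rate can be recovered from the two variables. The time-based primary endpoint and the sample size are untouched.

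This rests on three assumptions: conversion is reported as the protocol lists it, both endpoints share one denominator, and no performance goal for technical success stands in the unseen text. If such a goal existed, the reading would matter and the question would need to be reopened.

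### Does the serious adverse event summary miss early events because its starting point is not defined?

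*Protocol*

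**What the plan says.** The Serious adverse events entry of the protocol's Secondary Endpoints section states: "All Serious Adverse Events (SAEs) from the start of the CorPath GRX procedure until the end of the study will be summarized". Follow-up, in the Study Summary, is stated as: "All subjects will be followed post-CorPath GRX PCI procedure through 72-hours post-procedure or hospital discharge, whichever occurs first".

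Three other entries supply time points that bear on when that window opens:

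- Primary Endpoint: "Time from Catheterization Lab Arrival to Device Activation (CLADA) by CorPath GRX System".
- Overall procedure time: "Defined as the time measured from sheath insertion to removal of the last device used to treat the culprit lesion".
- Access to device activation: "Time from initial sheath insertion to device activation".

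The MACE entry is framed by hospital stay and not by the robotic procedure: "Completion of the STEMI procedure without in-hospital major adverse cardiovascular event MACE". Its components begin "MACE is defined as cardiac death, clinically driven target vessel revascularization (TVR) by repeat PCI" and go on to target-vessel bypass surgery and stent thrombosis.

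The pages available are numbered 6 to 9 of 34 and hold the study summary only.

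**The concern.** The safety window opens at an event that these pages do not name. Two readings are open. If the procedure starts at sheath insertion, a serious event between cath lab arrival and access is not summarized. If it starts at the first robotic step, a serious access complication before that step is not summarized either. Read literally, a subject who was enrolled but in whom the robotic procedure never began would have no window at all.

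The protocol treats time before device activation as its main outcome, so a reader may want the safety summary to cover the same minutes. MACE would not fill the gap for serious bleeding, vascular injury or arrhythmia. If sites read the start differently, the same event could count at one site and not at another. An event that was never collected cannot be restored at the analysis stage.

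**Working it through.** The plan states no figure on this point, so the check is to set the protocol's time points side by side. The order below assumes that sheath insertion follows cath lab arrival and precedes device activation.

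| Time point | Where the protocol uses it |
|---|---|
| First medical contact | opens the contact-to-activation secondary endpoint |
| Cath lab arrival | opens the primary endpoint (CLADA) |
| Sheath insertion | opens overall procedure time and both access intervals |
| Device activation | closes CLADA, the contact-to-activation interval and one access interval |
| Removal of last device | closes overall procedure time |
| 72 hours or discharge, whichever is first | closes follow-up |

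**Time left uncovered.** On this ordering,

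CLADA = (arrival to sheath) + (sheath to activation).

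- Start read as sheath insertion: uncovered time = CLADA − (sheath to activation) = arrival to sheath.
- Start read as the first robotic step, at the latest device activation: uncovered time is at most the whole of CLADA.
- The two readings therefore differ by at most the access-to-activation interval. That is the stretch in which an access complication would fall.

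**Size.** The pages give no expected value for any of these intervals and no serious event rate, so the number of events affected cannot be calculated. As a scale only, one omitted subject among the maximum of 100 is 1/100 = 1 percentage point; among an assumed 50 it is 1/50 = 2 points. Confidence limits around such a count would describe the sampling uncertainty of an assumed event rate. They would not measure what the window leaves out.

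**Which reading the text favours.** Overall procedure time is the only entry that says where a procedure interval begins, and it begins at sheath insertion. On that reading, access-phase events are counted and only the pre-access minutes are not.

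**What else covers those minutes.** Cardiogenic shock and cardiac arrest are exclusion criteria. In-hospital MACE is not tied to the procedure start, so cardiac death, target vessel revascularization and stent thrombosis may still be captured. Late consequences of any delay appear after the start and are inside the window.

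**Does the primary endpoint's origin matter?** CLADA measures how quickly the team reaches activation. The adverse event summary describes safety during and after the device procedure. Nothing in the document requires one origin for both. The contact-to-activation endpoint starts earlier still, and that gives no reason to summarize serious events from first medical contact.

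**Subjects with no robotic start.** Whether such subjects are enrolled depends on the point of enrolment, which these pages do not give. Need for thrombectomy and unsuitable coronary anatomy are exclusions. If they are judged at angiography, after access, many of these patients would never be enrolled subjects.

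**The case for a change.** The strongest case for a change is that the wording is product-specific and is never equated with overall procedure time. The document uses several terms for the procedure without linking them, and the first robotic step is a fair reading. Because sheath insertion and device activation are separate time points with their own endpoint between them, the reading decides whether a serious access-site event counts. The remedy is cheap, at one definition and one sentence, and a later analysis plan cannot recover events that sites did not record.

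Part of this stands. The opening event is not named in the pages available, and naming it would remove a doubt about access-phase events. The rest is weaker:

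- A synopsis line that uses a term without defining it is not an error when most of the 34 pages, where reporting periods are normally set out, are not available.
- Different counting across sites is possible but not shown, since no case report form or reporting instruction is visible.
- Opening the window at cath lab arrival, or at consent if later, is not clearly better. If consent came after arrival, the window would still not match CLADA. If consent came after the procedure had started, the window would open later than it does now, and splitting events into before and after could not restore the present summary.

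**Conclusion.** The concern does not call for a change. It comes down to one undefined term in a synopsis, for which the same section offers a sensible meaning, sheath insertion. On that meaning the uncovered time is arrival to sheath insertion, and the events at issue are non-MACE serious events in that stretch. Their number cannot be derived from the document, and nothing shows that a result would change. The different origin of the primary endpoint is a legitimate design choice, and the gap for subjects without a robotic start rests on an enrolment point that is not shown.

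This conclusion assumes that analysts and sites take the start as sheath insertion, in line with the overall procedure time entry, or that the body of the protocol names the event. If the body instead fixed the start at the first robotic step, access complications before that step would be left out of the summary, and the question would deserve a second look.
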